### **Follow-up of Adverse Events**

All investigators should follow up subjects with AEs until the event is resolved or until, in the opinion of the investigator, the event is stabilized or determined to be chronic. Details of AE resolution must be documented in the eCRF.

#### **10.1.2.1.3 Serious Adverse Events**

##### **Serious Adverse Event Definition**

An AE is considered an SAE if it:

- a) led to death,
- b) led to serious deterioration in the health of the subject, that either resulted in
  - 1) a life-threatening illness or injury, or
  - 2) a permanent impairment of a body structure or a body function, or
  - 3) in-patient or prolonged hospitalization, or
  - 4) medical or surgical intervention to prevent life-threatening illness or injury or permanent impairment to a body structure or a body function,
- c) led to fetal distress, fetal death or a congenital abnormality or birth defect.

Note: Planned hospitalization for a pre-existing condition, or a procedure required by the protocol, without serious deterioration in health, is not considered an SAE.

##### **Serious Adverse Device Effect (SADE)**

An SADE is an adverse device effect that has resulted in any of the consequences characteristic of an SAE.

##### **Reporting of Serious Adverse Events**

All device- or surgery-related SAEs must be entered into the EDC system within 24 hours of being notified of the event. The sponsor will be notified by EDC system once the SAE electronic form has been submitted.

The relationship of the clinical event to the devices and procedure should be reported on the Serious Adverse Event Form for Devices and will be determined by the investigator.

Following evaluation of each SAE, the responsible IEC/IRB will be notified as appropriate based on national regulations.

All SAEs that occur from the time the informed consent form (ICF) is signed through to their final study visit must be reported to the sponsor. In addition to entering the information into the EDC system, the investigator must:

- Notify the sponsor immediately (within 24 hours) by fax using the Serious Adverse Event Form for Devices. The form should be sent directly to the sponsor at [LC-Medical\\[contact]](mailto:[contact]) or fax to [contact] or [contact]. The SAE report should be completed regardless of the amount of information available although the investigator is expected to provide as much information as possible.
- Obtain and maintain in his/her files all pertinent medical records, information, and medical judgments from colleagues who assisted in the treatment and follow-up of the subject.
- Provide the sponsor with a complete, written case history (AE report form) which includes a statement as to whether the event was or was not related to the use of the investigational device or procedure.

The sponsor (or its representative) will report all SAEs associated with the use of the study device to the regulatory agencies (IEC/IRB, Competent Authorities) as appropriate according to relevant SOPs and to the national laws of the country where the trial is performed.

For every SAE, appropriate measures should be taken to treat/resolve and monitor the subject. The investigator should keep Allergan closely informed of the progress as related to the SAE. Any subjects who are withdrawn from the study due to an AE shall still be followed up until the outcome is resolved.

## **10.2 Data Safety Monitoring Board**

Not applicable

### **10.2.1 Appropriateness of Measurements**

The effectiveness and safety assessments planned for this study are widely used and generally recognized as reliable, accurate and relevant to the disease condition.

## **11 STATISTICAL METHODS**

Prior to database lock a statistical analysis plan (SAP) defining all details of analysis will be prepared and finalized.

### **11.1.1 Datasets or Populations Analyzed**

The Enrolled population consists of all study eyes for which the subject has signed the ICF. The Enrolled population will be used to summarize disposition data.

The Intent-to-treat (ITT) population consists of all enrolled eyes randomized to study glaucoma surgery (XEN or trabeculectomy). The ITT population will be the primary analysis population for effectiveness data. Subject demographics, baseline characteristics, and PRO data will be analyzed using the ITT population. Subjects will be grouped and analyzed according to the actual surgery received.

The Modified Intent-to-treat (mITT) population consists of eyes in the ITT population that receive study glaucoma surgery and have no major protocol deviations, which will be defined in the SAP and identified prior to database lock. The mITT population will be used for selected effectiveness endpoints (as specified in the SAP), and will be used for the analyses of PRO data also.

The Safety population consists of all enrolled eyes that undergo study glaucoma surgery, whether surgery is completed or aborted, and have follow-up visits or evaluations. The Safety population will be used to analyze AEs, medical and ophthalmic history, and concomitant medications (ocular and systemic). Subjects will be grouped and analyzed according to the surgery they received.

### **11.1.2 Demographic and Other Baseline Characteristics**

Demographic and baseline subject characteristics will be summarized. Descriptive statistics (such as mean, SD, minimum, median, and maximum) will be presented for each continuous variable. Categorical variables will be displayed using frequency counts and percentages.

### **11.1.3 Effectiveness Variables and Statistical Analyses**

#### **Definition of Primary Effectiveness Endpoint**

The primary endpoint for the study will be the percentage of subjects achieving  $\geq 20\%$  mean IOP reduction from baseline at Month 12 on the same or fewer number of topical IOP-lowering medications, without clinical hypotony, loss of vision to count fingers, or secondary glaucoma surgical intervention.

## **Definition of Secondary Effectiveness Endpoints**

Effectiveness will be determined by comparing the medicated preoperative IOP with the postoperative IOP at Month 12, and the number of topical IOP-lowering medications at screening with number of topical IOP-lowering medications at Month 12. Individual secondary effectiveness endpoints are defined in [Section 7.2](#).

## **Definition of Performance Endpoints (Device Studies)**

The IOP change at all visit windows will be summarized by mean, SD, median, maximum, and minimum. The percentage change in IOP from baseline to Month 12 will also be summarized descriptively. When necessary, appropriate parametric or nonparametric analyses will be used to determine statistically significant differences.

## **Methods of Statistical Analysis**

The number and proportion of subjects achieving  $\geq 20\%$  mean IOP reduction from baseline at Month 12 on the same or fewer number of topical IOP-lowering medications, without clinical hypotony, loss of vision to count fingers, or secondary glaucoma surgical intervention will be tabulated with 95% CI calculated by using the normal approximation method. The difference of the proportions will be estimated and the 95% CI of the difference will also be calculated with the method of the normal approximation. The 2 treatment groups will be claimed as equivalent if the 95% CI of the differences is within the -18% to 18% interval. The least squares mean change from baseline in IOP and the least squares mean difference between the 2 treatment groups will be estimated using the analysis of covariance (ANCOVA) model or the mixed-effect model repeat measurement (MMRM) model. The proportion and 95% CI of complete success and qualified success will be calculated with normal approximation.

### **11.1.4 Safety Variables**

All reported treatment-emergent AEs (TEAEs), treatment-related TEAEs, SAEs, and all safety measures collected will be tabulated by counts and percentages. Adverse events will be summarized by presenting the number and percentage of subjects having any AE. Any other information collected (such as AE severity) will be tabulated and listed as appropriate. Pregnancy of female subjects should also be tabulated. Analyses of AEs and other safety variables will be described in the SAP.

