**Study Design:**

Multicenter, randomized, parallel-group, prospective, open-label

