## **10 EFFECTIVENESS AND SAFETY VARIABLES**

### **10.1 Effectiveness and Safety Measurements Assessed**

#### **10.1.1 Effectiveness Variables**

##### **10.1.1.1 Intraocular Pressure**

Every attempt should be made to schedule the visits at approximately the same time of day to avoid the influence of diurnal fluctuations on study procedures, specifically measurement of IOP.

Except at the Operative Visit (Visit 2), IOP will be measured at all study visits by standard Goldmann applanation tonometry. The readings will be recorded on the appropriate eCRF. The tonometer should be checked for proper calibration monthly and the date of calibration checking should be recorded. The eye cannot have received pupil-dilating medications.

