##### **Adverse Event**

An AE is defined in accordance with ISO 14155 as any untoward medical occurrence, unintended disease or injury, or untoward clinical signs (including abnormal laboratory findings) in subjects, users or other persons, if related to the investigational medical device. This definition includes events related to the investigational medical device or comparator and events related to the procedures involved. Disease signs and symptoms that existed prior to the study treatment are not considered AEs unless the condition recurs after the participant has recovered from the pre-existing condition or the condition worsens in intensity or frequency during the study.

AEs will be monitored throughout the study beginning with the Preoperative Visit. At each postbaseline visit, the investigator will begin querying for AEs by asking each participant a general, nondirected question such as “Have you had any changes to your condition since your last visit?” Previous AEs and changes in therapy/concomitant medications are to be updated. Directed questioning and examination will then be done as appropriate. All reportable AEs and clinically significant abnormal laboratory findings will be documented on the appropriate eCRF.

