#### **10.1.2.1.2 Possible Adverse Events**

The following is a list of AEs that can occur intraoperatively during implantation of XEN and/or trabeculectomy surgery. These and any other AEs that occur should be reported in the AE eCRF:

- Detached Descemet’s membrane
- Iris damage
- Lens contact
- Vitreous bulge or loss
- Anterior chamber bleeding
- Retrobulbar hemorrhage
- Conjunctival perforation

- Conjunctival or scleral flap tearing
- Shallow anterior chamber with peripheral iridocorneal touch
- Flat anterior chamber with iridocorneal touch extending to the pupil
- Device malfunction identified prior to implantation
- Choroidal hemorrhage or effusion

The following is a list of AEs that can occur postoperatively for XEN and/or trabeculectomy surgery. These and any other AEs that occur should be reported in the AE eCRF:

- Angle recession
  - Anterior chamber shallow with peripheral iridocorneal touch
  - Anterior chamber flat with iridocorneal touch
  - BCVA loss of  $\geq 2$  lines ( $\geq 10$  Early Treatment Diabetic Retinopathy Study [ETDRS] letters)
    - $\leq 30$  days
    - $>30$  days
    - At 12 months (persistent loss)
  - Bleb leak (without operative room or slit lamp revision)
  - Bleb leak (with operative room or slit lamp revision)
  - Blebitis (with or without anterior chamber reaction or hypopyon)
  - Cataract formation
  - Clinically significant progression of cataract, based on an assessment by the investigator
  - Choroidal effusion (extending posterior to equator, without blood)
  - Choroidal effusion (obscuring disc or macula, without blood)
  - Choroidal effusion (with choroids touching in the center of the eye, without blood)
  - Choroidal effusion (extending posterior to equator, with blood)
  - Choroidal effusion (obscuring disc or macula, with blood)
  - Choroidal effusion (with choroids touching in the center of the eye, with blood)
  - Choroidal effusion and/or hemorrhage occurring  $>30$  days (persistent)
  - Chronic pain (present greater than 3 months)
  - Corneal edema grade 3 or grade 4 ( $>30$  days postoperatively)
  - Cyclodialysis
  - Dellen
  - Device malfunction
  - Endophthalmitis
  - Fixed dilated pupil
  - Hyphema ( $\geq 2$  mm in height [layered] at any time)
  - Hyphema (present or arising  $>30$  days)
  - Hypotony (IOP  $<6$  mm Hg at any time)
-

- Persistent hypotony (IOP <6 mm Hg at 2 visits >30 days apart)
- Hypotony maculopathy
- Implant exposure
- Implant fracture
- Implant migration

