5.6.2. Adverse Events

Adverse events will be coded by system organ class (SOC) and preferred term (PT) using the Medical Dictionary for Regulatory Activities (MedDRA), version #21.0 or newer.

Adverse events will be classified to either ocular AEs or nonocular AEs. An ocular AE will be determined as indicated on the AE form of eCRF, and thus are not limited to AEs with primary SOC of eyes. The adverse events will be also classified to either AE or adverse device effect (ADE). The summary of AEs will be separately done for nonocular AEs, ocular AEs and ADEs. Ocular AEs and ADEs will be tabulated by treatment group for the study, and nonocular AEs will be summarized by treatment group for participants. eye

An AE will be considered a treatment emergent adverse event (TEAE) if the AE began or worsened (increased in severity or became serious) on or after the date (and time, if known) of the surgery.

An TEAE and ADE will be considered a TESA or SADE if it meets any SAE criterion.

Overall summary of TEAEs will be provided for categories of all TEAEs, treatment-related TEAEs/TEADEs, TESA/TEADE, deaths, TEAEs/TEADEs leading to study discontinuation, TEAEs/TEADEs, treatment-related TEAEs/TEADEs, TESA/TEADEs and TEAEs/TEADEs leading to study discontinuation will be further classified into ocular and nonocular subcategories.

The number and percentage of participants reporting TEAEs/TEADEs in each treatment group will be tabulated by SOC in descending frequency order of XEN first, then by preferred term in descending frequency order of XEN, and further categorized by severity. If more than 1 AE/ADE is coded to the same preferred term for the same participant, the participant will be counted only once for that preferred term using the greatest severity and strictest causality for the summarization by severity and causal relationship.

The number and percentage of participants with treatment-related TEAEs/TEADEs will be tabulated by SOC and preferred term.

Summary tables will be provided for participants with TESA and participants with TEAEs/TEADEs leading to discontinuation. Listings of all AEs, SAEs, and AEs leading to discontinuation by participant will be presented.

The same analysis will be repeated for ocular TEAEs/TEADEs, ocular TESA/TEADEs.

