5.6.2.1. Adverse Events of Special Interest

Intraoperative AEs

- Detached Descemet's membrane
- Iris damage
- Lens contact
- Vitreous bulge or loss
- Anterior chamber bleeding

CONFIDENTIAL

Draft Statistical Analysis Plan v2.0

XEN-45 Gel Stent

- Retrobulbar hemorrhage
- Conjunctival perforation
- Conjunctival or scleral flap tearing
- Shallow anterior chamber with peripheral iridocorneal touch
- Flat anterior chamber with iridocorneal touch extending to the pupil
- Device malfunction identified prior to implantation
- Choroidal hemorrhage or effusion

Postoperative AEs

The following is a list of AEs that can occur postoperatively for XEN and/or trabeculectomy surgery.

- Angle recession
- Anterior chamber shallow with peripheral iridocorneal touch
- Anterior chamber flat with iridocorneal touch
- BCVA loss of ≥ 2 lines (≥ 10 Early Treatment Diabetic Retinopathy Study [ETDRS] letters)
- ≤ 30 days
- > 30 days
- At 12 months (persistent loss)
- Bleb leak (without operative room or slit lamp revision)
- Bleb leak (with operative room or slit lamp revision)
- Blebitis (with or without anterior chamber reaction or hypopyon)
- Cataract formation
- Clinically significant progression of cataract, based on an assessment by the investigator
- Choroidal effusion (extending posterior to equator, without blood)
- Choroidal effusion (obscuring disc or macula, without blood)
- Choroidal effusion (with choroids touching in the center of the eye, without blood)
- Choroidal effusion (extending posterior to equator, with blood)
- Choroidal effusion (obscuring disc or macula, with blood)
- Choroidal effusion (with choroids touching in the center of the eye, with blood)
- Choroidal effusion and/or hemorrhage occurring > 30 days (persistent)
- Chronic pain (present greater than 3 months)
- Corneal edema grade 3 or grade 4 (> 30 days postoperatively)
- Cyclodialysis
- Dellen
- Device malfunction
- Endophthalmitis
- Fixed dilated pupil
- Hyphema (≥ 2 mm in height [layered] at any time)
- Hyphema (present or arising > 30 days)
- Hypotony (IOP < 6 mm Hg at any time)

CONFIDENTIAL

Draft Statistical Analysis Plan v2.0

XEN-45 Gel Stent

- Persistent hypotony (IOP <6 mm Hg at 2 visits >30 days apart)
- Hypotony maculopathy
- Implant exposure
- Implant fracture
- Implant migration
- Implant obstruction (complete or partial)
- Implant repositioning requiring surgical intervention
- Increase in cup/disc ratio of ≥ 0.3 units on slit lamp examination

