5.6.3.5. Pachymetry

The central corneal thickness in microns will be collected. The mean change from baseline in the study eye will be summarized using descriptive statistics.

CONFIDENTIAL

Draft Statistical Analysis Plan v2.0

XEN-45 Gel Stent

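### In an open-label trial, three threshold-defined complications and two-line vision loss by period have no measurement-derived count in the SAP text

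*Protocol*

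**What the plan says.** The synopsis describes the design as "Multicenter, randomized, parallel-group, prospective, open-label", so whoever files an AE knows which operation was done.

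Protocol 10.1.2.1.2 lists possible intraoperative and postoperative complications and instructs sites: "These and any other AEs that occur should be reported in the AE eCRF". Several list items are defined by a recorded value. SAP 5.6.2.1 repeats the list, for example "Persistent hypotony (IOP <6 mm Hg at 2 visits >30 days apart", and gives no rule for deriving any item from data. The counting rule is in SAP 5.6.2: "The number and percentage of participants reporting TEAEs/TEADEs in each treatment group will be tabulated by SOC in descending frequency order of XEN first".

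The underlying measurements are collected. Outside the operative visit, Protocol 10.1.1.1 states that "IOP will be measured at all study visits by standard Goldmann applanation tonometry". Acuity and pachymetry also have their own SAP analyses:

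- SAP 5.4.2 makes eyes with IOP of 6 mm Hg or less at any time point a safety endpoint.
- SAP 5.6.3.3 counts participants by worst line change across follow-up, from the visual acuity eCRF page. Worsening is below −2 lines, and no change runs from −2 to 2.
- SAP 5.6.3.5 says of corneal thickness: "The mean change from baseline in the study eye will be summarized using descriptive statistics".

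Protocol 11.1.4 says "All reported treatment-emergent AEs (TEAEs), treatment-related TEAEs, SAEs, and all safety measures collected will be tabulated by counts and percentages" and leaves the details to the SAP. Protocol 10.1.2 likewise promises frequencies at each visit for all safety measures.

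**The concern.** A rise in IOP of 10 mm Hg, or two readings below 6 mm Hg more than 30 days apart, can be read straight from the database. If such an event is counted only when someone files it, the count mixes how often it happened with how often it was written up. Investigators here know the arm. The protocol (6.2.2) also records an expectation of fewer complications with XEN than in published trabeculectomy studies. The AE definition carries the condition "if related to the investigational medical device". The next sentence extends it to the comparator and to procedures, but deciding whether a reading is an AE still takes judgement.

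Comparing safety is half of the trial's stated objective. If filing is less complete in one arm, these rows can show a difference that is not there or hide one that is. The recorded values could settle the matter, but nothing in the SAP text asks for that comparison.

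**Working it through.** The plan states no figure on this point, so there is none to reproduce. The check has three parts.

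**1. Listed events against measurement-based analyses**

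| Listed event (Protocol 10.1.2.1.2, SAP 5.6.2.1) | Nearest analysis of recorded values | What it does not give |
|---|---|---|
| IOP increase of 10 mm Hg or more from baseline | IOP and IOP change summarised by visit (Protocol 11.1.3, 11.1.6) | A count of eyes reaching the threshold |
| IOP below 6 mm Hg at 2 visits more than 30 days apart | Eyes at 6 mm Hg or less at any time point (SAP 5.4.2) | Persistence; the cut also differs (≤6 against <6) |
| Corneal thickness up 10% or more with corneal edema | Mean change in thickness (SAP 5.6.3.5) | A count, and the link to edema |
| BCVA loss of 2 lines or more: up to 30 days, after 30 days, at 12 months | Worst line change, all follow-up pooled (SAP 5.6.3.3) | A loss scored exactly −2, and its timing |

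The first three events have no measurement-derived count. The fourth has one, but it does not match the listed event.

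**2. The BCVA cut**

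SAP 5.6.3.3 sets line change = 10 × [log10(20/d_follow-up) − log10(20/d_baseline)], with each logarithm rounded to the nearest tenth.

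- 20/20 to 20/30: 10 × (−0.2 − 0.0) = −2.0, no change
- 20/25 to 20/40: 10 × (−0.3 − (−0.1)) = −2.0, no change
- 20/50 to 20/80: 10 × (−0.6 − (−0.4)) = −2.0, no change
- 20/20 to 20/40: 10 × (−0.3 − 0.0) = −3.0, worsening

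Because the logarithms are rounded to tenths, the result is always a whole number. A cut below −2 therefore starts at a 3-line loss. The AE list and the clinical hypotony definition (SAP 5.3.1) both use 2 lines or more.

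**3. What unequal filing could do**

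The event and filing rates below are assumptions; the documents give neither. With the same true rate p in both arms and filing proportions r_X (XEN) and r_T (trabeculectomy), the expected false difference is p × (r_X − r_T).

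| Filing, XEN / trabeculectomy | p = 10% | p = 20% | p = 30% |
|---|---|---|---|
| 90% / 60% | +3 points | +6 | +9 |
| 60% / 90% | −3 points | −6 | −9 |
| 70% / 90% | −2 points | −4 | −6 |
| 50% / 100% | −5 points | −10 | −15 |

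At 90% against 60% the reported ratio is 0.9/0.6 = 1.50, and reversed it is 0.67; the true ratio is 1.00. With the planned enrolment of 76 and 38 (SAP 3) and p = 20%, the expected filed counts are 76 × 0.20 × 0.9 = 13.7 against 38 × 0.20 × 0.6 = 4.6, or 9.1 against 6.8 if the filing rates are swapped. Counting from the measurements would give an expected difference of 0.

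For scale, the sampling half-width at 76 and 38 is 1.96 × √[p(1−p)(1/76 + 1/38)]. That is about 12 points at p = 10% and about 16 points at p = 20%.

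**The case against.** The case against has real weight.

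- **Filing is instructed.** Protocol 10.1.2.1.2 tells sites to report the listed events, 12.2 has the monitor check forms against source, and 12.3 has inconsistent data queried. These controls lower the risk. They do not remove it, because no stated rule compares IOP, BCVA or pachymetry values with the AE form.
- **Much is already counted from data.** Low IOP at any time point and BCVA worsening are measured. SAP 5.6.3.2 plans counts of biomicroscopy and ophthalmoscopy changes. The clinical hypotony steps start from measured IOP and acuity, although the last also uses reported AEs. A reader might infer that every threshold complication, vision loss included, is counted only if an AE is filed. The documents do not support that.
- **The protocol promises frequencies for all safety measures.** So the gap lies in the SAP not carrying this out. Table specifications are in a separate document (SAP 1) and may add such counts, so the point can be made only about the SAP text.
- **The assumed effects are mostly small against sampling error.** All the scenarios at true rates of 10% and 20% lie within the half-widths above, and the safety tables are descriptive. This stands, but unequal filing shifts the estimate and the interval does not reveal it.
- **Derivation is not automatic.** The thickening event needs edema, a clinical finding. SAP 5.1 defines two IOP baselines. Postoperative pachymetry timing cannot be read from the extracted schedule, although SAP 5.6.3.5 presupposes such values. The measurements are themselves taken unmasked. The fix has to allow for these points.

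**Conclusion.** The concern holds in a limited form. In the SAP text, IOP rise, persistent hypotony and corneal thickening with edema reach the safety tables only through AEs filed by unmasked investigators. For vision loss, a recorded count exists, but its cut and its pooling over follow-up leave the exact 2-line loss, and the split by period, visible only through AE forms.

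The size is unknown. The 2–15 point range rests wholly on assumed event and filing rates, and the sign reverses if filing is more complete in the other arm. A reader might infer that the plan favours XEN, or that under-reporting has happened; nothing in the documents shows either. Nor do they support letting derived counts replace the AE tables, since a filed AE also carries clinical judgement that a threshold cannot.

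This is a low-cost improvement to the safety reporting. It does not challenge the primary analysis.

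**What to change.** Amend SAP 5.6.2.1, 5.6.3.3 and 5.6.3.5 as follows.

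1. **Add a by-arm table derived by program** from all recorded postoperative values, at the thresholds already listed: IOP rise of 10 mm Hg or more; IOP below 6 mm Hg at two visits more than 30 days apart; BCVA loss of 2 lines or more; thickness up 10% or more with recorded corneal edema. Use every recorded value, because SAP 6.5.1 keeps only one per visit window. State where edema is taken from. If its only source is the AE form, say that this row still depends on filing.
2. **Change BCVA worsening to −2 or worse**, with no change starting above −2. Report it up to 30 days, after 30 days and at Month 12. Round the line change before comparing, so that machine precision does not move an exact −2.
3. **Name the IOP baseline.** Use the preoperative baseline of SAP 5.1. Also show the count from the medicated baseline, because medication may be stopped before surgery (Protocol 8.4.5) and the two can then differ.
4. **Show derived counts beside AE-form counts** and list the eyes where they disagree.

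The thresholds are already written and the recorded measurements are already due for analysis. The cost is SAP wording and modest programming. Counts will probably rise in both arms, so a footnote should explain the two sources.
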